Appendix III: Dry Eye Classification Criteria and Appendix V: Staging the Severity of MGD-Related Ocular Surface Disease

17. General statistical methods and types of analyses

- Comparisons, ANOVA, meibomian secretion scores, meibomian gland dropouts, OSDI
- The primary visit is week 4 and primary efficacy variables are the FTBUT and quality of meibomian secretions
- A two-sided test with p-value less than or equal to 0.05 will be considered as statistically significant.
- 18. Comparisons between pairs of treatment groups will be done with Cochran-Mantel Haenszel (CMH) tests, stratified by the ocular discomfort strata. Within Strata comparisons will be done with Wilcoxon rank-sum tests for both ordinal and continuous variables. For nominal variables, within strata comparisons will be done with Pearson's chi-square or Fisher's exact tests.
- 19. Exploratory pharmacokinetics data analysis
- Summary statistics of testosterone, dihydrosterosterone, and 3-alphaandrostanediol glucuronide serum concentrations will be calculated. The relationships between treatment time and gender will be examined.

Confidentiality

The identity of the subjects will be treated as confidential. The results of the study, including any other data, may be published for scientific purposes but will not reveal the name of the subject or include any identifiable references to the subject. Although

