In contradistinction, the studies by Worda et al⁸ and Connor et al.^{16-21,26,31} have examined topical eyelid androgen application with generally favorable effects on tear film parameters and also a good safety profile. However, the eyelid application studies were not consistent in the subject type (e.g., both males and females were not uniformly enrolled), the androgen status and serum levels were not assessed prior to, or following androgen application and the studies were only published as peer-reviewed abstracts and mostly were done in one laboratory. This prospective randomized, controlled double masked study aims to evaluate the efficacy and safety of topical transdermal application to the eyelids of low dosage androgen in a population of patients with evaporative dry eye associated with meibomian gland dystrophy and aqueous tear deficient dry eye.

Methods

Study objective

To evaluate the safety and efficacy of an FDA-approved androgen nasal supplement (Natesto, Acerus Pharmaceuticals Corporation, 4.5% gel concentration) in males and females with dry eye of either aqueous tear deficiency or evaporative subtype.

Clinical hypothesis

- Natesto applied to upper and lower eyelid skin is more effective than placebo as measured by fluorescein tear breakup time (TBUT) and mean scores for meibomian secretion quality at 4 weeks and overall ocular comfort at 8 weeks.
- Natesto has an acceptable safety profile in ocular structures and general systemic system.

Statistical Hypotheses:

H₀: There is no difference in change from baseline to week four for either fluorescein breakup time (TBUT) or meibomian secretion score (0 - 24 scale) between the test and placebo-treated sample.

 H_A : There is a difference in the change from baseline to week four for either fluorescein breakup time (TBUT) or meibomian secretion score (0 – 24 scale) between the test and placebo-treated sample

Overall study design

Structure

We propose a randomized controlled trial (RCT) of one month duration dosing BID with

an FDA-approved androgen nasal supplement (Natesto, Acerus Pharmaceuticals

Corporation, 4.5% gel concentration) in males and females with dry eye of either aqueous tear deficiency or evaporative subtype.

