- Comparison of National eye Institute (NEI) to Ocular Staining Score (OSS) (DEWS II recommendation) staining scheme for efficiency
- 2. Repeatability of the above two staining schemes and meibomian gland secretion scores

Pharmacokinetic measures

• The patients will have blood samples (20 ml) drawn for the determination of total serum testosterone. Blood will be drawn at baseline and within two hours of dose application at Week 4 visit.

Safety measures

- Adverse events (treatment related and treatment unrelated)
- Visual acuity (BCVA ETDRS)
- Biomicroscopy
- Ophthalmoscopy exam
- IOP
- Male scalp hair evaluation
- Female hair evaluation (upper lip, chin, cheeks, scalp)

Subjects

Subjects will consist of a convenience sample of patients over 18 years old with signs and symptoms of dry eye disease (DED). Moderate to severe dry eye subjects who have either aqueous tear deficiency or evaporative dry eye related to meibomian gland

dysfunction will be recruited. The diagnosis of DED is made according to the DEWS II diagnostic criteria based on:

- 1. DE symptomatology: OSDI score \geq 13 and Modified Schein score \geq 7.5
- 2. Plus one of the following:
 - a. NIBUT < 10 seconds or fluorescein breakup time ≤ 6.0 seconds or
 - b. Osmolarity \geq 308 mosm/L in either eye or intraocular difference > 8 mosm/L or
 - Ocular surface staining (SICCA scale) > 5 corneal spots, > 9 conjunctival spots
 - d. Conjunctival-corneal epithelial damage (fluorescein, rose bengal, or lissamine green staining score >3 points).
- 3. Subtype Tests: severity according to the DEWS II Dx report;⁴ page 556
 - a. Aqueous tear deficiency: non-invasive meniscus height (TMH) ≤ 0.2 mm
 - b. Evaporative: only moderate to severe included:
 - Moderate: 1) orifice plugging, 2) lid margin vascularity, 3) gland secretion grade 8 – 12 (central 8 glands, 0 – 3 scale each),
 4) expressibility grade 2
 - Severe: 1) lid margin dropout or displacement, 2) gland secretion score ≥ 13, 3) expressibility grade of 3

The subjects will be recruited from among students, staff, faculty and patients from Ketchum Health, the clinical facility at Marshall B. Ketchum University. Additionally, the study will be advertised on social media to maximize the recruitment pool, such as Facebook, Instagram, and Twitter. Subjects will be sex-, and age-matched as they are enrolled since these parameters affect dry eye parameters such as marginal changes and meibomian gland secretion. ⁴⁴

Sample size estimation

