- In this present investigation the principal outcome measures, fluorescein TBUT (using 2.0 microliters of 1.0% sodium fluorescein) and the system for meibomian gland secretion (0-24 scale) are recommended by the MGD workshop and DEWS II diagnostic committees.⁴ Table 2 shows the sample size estimation with two arm parallel design, comparing the change from baseline in FTBUT in each arm with a two sample t-test continuous data, clinically meaningful change of 2.5 seconds with Standard Deviation (SD) following treatment of 2.5 seconds. The results are as follow:
- 2-Sample t Test
- Testing mean $1 = \text{mean } 2 \text{ (versus } \neq \text{)}$
- Calculating power for mean 1 = mean 2 + difference
- $\alpha = 0.05$
- Assumed standard deviation = 2.5

Table 2: Sample size estimation

_	Difference	Sample Size	Target Power	Actual Power
	2.0	26	0.8	0.807487
	2.5	17	0.8	0.807037
	3.0	12	0.8	0.802079
	3.5	10	0.8	0.841306

4.0

0.8

0.844793

- 2.
- 3. With the actual power of 0.807, total of 34 subjects with seventeen (17) subjects per arm will be recruited for this study.

8

Randomization method

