Due to the relatively small sample size (n < 200) and the need to control and balance the influence of covariates, such as age and sex, we adopted the method of covariate adaptive randomization.⁴⁵ With two covariates of sex (2 levels: male, female) and age (2 levels: <50, >50) between study arms (treatment and control), a total of 4 block combinations is produced. After a participant has passed the screening and day 0 examinations, the first 10 participants will be assigned to one of the treatment groups within each block by simple randomization, according to a randomization scheme ([name] [name] will generate this). The next new participant is then sequentially assigned to a particular treatment group by considering the specific covariates and previous assignments of participants. For example, the first 10 participants assignment are broken down by covariates as in Table 3. Then the 11^{th} participant, who is male and >50 years old, needs to be assigned to a group (control vs. treatment). Based on the characteristics of the 11th participant, the method adds marginal totals of the corresponding covariate categories for each group and compares the totals. The participant is assigned to the group with the lower covariate total to minimize imbalance. In this example, the appropriate categories are male and > 50 years old, which results in a total of 6 (3 for male and 3 for >50) for the control group and a total of 5 (3 for male and 2 for >50) for the

treatment group. Because the sum of marginal totals is lower in treatment group

(5<6), the 11th participant is assigned to the treatment group.

Control group		Sex	Marginal total	
		Male	Female	
Age	<50	2	0	2
	>50	1	2	3
Marginal total		3	2	5

Table 3. Procedure of randomization

Treatment group		Sex	Marginal total	
		Male	Female	
Age	<50	1	2	3
	>50	2	0	2
Marginal total		3	2	5

Every participant is assigned a number from 001 to 100 and recorded with the specific number during the whole study until de-identified at the end of the study.

Masking

- 1. The participants will be masked from the assignment of the treatment group.
- An unmasked research assistant will recruit and schedule subjects and administer the questionnaires and exclude subjects based on the above-mentioned inclusion and exclusion criteria.
- 3. Another unmasked research assistant will implement the randomization based on the above covariate adaptive randomization method.

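### The between-arm CMH test is stratified by ocular discomfort strata that are never defined, and no test is designated primary for FTBUT or meibomian secretion score

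*Combined protocol and SAP*

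**What the plan says.** Under General statistical methods and types of analyses, the primary visit is week 4, the primary variables are FTBUT and meibomian secretion quality, and the two-sided level is 0.05. Three kinds of test then appear in the same section:

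- a fragment reading "Comparisons, ANOVA, meibomian secretion scores, meibomian gland dropouts, OSDI", which includes the secretion score but not FTBUT;
- item 18: "Comparisons between pairs of treatment groups will be done with Cochran-Mantel Haenszel (CMH) tests, stratified by the ocular discomfort strata";
- item 18 again: "Within Strata comparisons will be done with Wilcoxon rank-sum tests for both ordinal and continuous variables".

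A fourth method appears only under Sample size estimation, described as "sample size estimation with two arm parallel design, comparing the change from baseline in FTBUT in each arm with a two sample t-test" and based on a "clinically meaningful change of 2.5 seconds with Standard Deviation (SD) following treatment of 2.5 seconds". It gives 17 per arm and power 0.807.

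The null hypothesis under Statistical Hypotheses is "There is no difference in change from baseline to week four for either fluorescein breakup time (TBUT) or meibomian secretion score" between the arms. Randomization method describes covariate-adaptive allocation: "With two covariates of sex (2 levels: male, female) and age (2 levels: <50, >50) between study arms". No symptom or discomfort factor is used there.

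**The concern.** A stratified test needs its strata. Item 18 names a stratification factor that appears nowhere else in the text available. The nearest candidates do not fill the gap:

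- Overall ocular comfort, in the clinical hypothesis, is an outcome at 8 weeks.
- The OSDI bands in the appendix severity table serve MGD staging and are not linked to item 18.
- The modified Schein score is a further possibility that nothing rules in or out.

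Someone will therefore have to choose the instrument, cut-points and visit, possibly with outcome data in view.

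No sentence says which named method decides the trial for FTBUT or for secretion score. The test that was sized is not listed in the analysis section, and the between-arm test that is listed was not sized. In a 34-subject trial these methods can give different verdicts on the same data.

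**Working it through.** **1. The plan's own figure.** Inputs from Sample size estimation: n = 17 per arm, difference 2.5 s, SD 2.5 s, two-sided alpha 0.05. The noncentrality is 2.5 / (2.5 × √(2/17)) = 2.915, on 34 − 2 = 32 degrees of freedom (critical t = 2.037). The noncentral t distribution gives power 0.8070, against the stated 0.807037. The other four rows of Table 2 also reproduce. The arithmetic is right, for an unstratified t-test on change.

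**2. The item 18 test at the same sample size.** The strata must be assumed. Subjects need OSDI of at least 13, so only three bands of the appendix table remain (13–22, 23–32, 33–100); two and three strata are used here. Data are normal with SD 2.5 and difference 2.5. Strata are equally likely and unrelated to outcome. The statistic is a van Elteren type CMH: ranks within each stratum divided by (stratum size + 1), summed over strata and referred to the normal distribution.

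| | t-test | rank CMH, 2 strata | rank CMH, 3 strata |
|---|---|---|---|
| Power | 0.81 | about 0.76 (runs 0.75–0.77) | about 0.73 |
| Disagrees with t-test on significance | – | about 9% | about 12% |

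With no true effect, taking whichever of the t-test and the rank CMH is significant gives a type I error of about 0.063–0.067 on one endpoint. Choosing among the t-test, unstratified Wilcoxon and both CMH versions gives about 0.08.

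Part of the power loss comes from ranking alone: the unstratified Wilcoxon has power of about 0.78–0.79. The loss also depends on the strata. A raw-score CMH has power 0.79 and 0.77 with two and three non-prognostic strata, but 0.81 and 0.83 if the strata differ in steps of 0.5 SD with total SD held fixed.

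**3. Within-strata Wilcoxon tests.** With two or three equal strata, exact Wilcoxon power in each stratum is about 0.42 or 0.24. A stratum with 3 per arm has a smallest exact two-sided p of 2/20 = 0.10. That limit applies only to the exact test: the large-sample version at complete separation gives 0.0495, or 0.081 with continuity correction. The plan does not say which version applies.

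**4. ANCOVA for FTBUT.** The model has treatment, baseline, sex and age group, leaving 34 − 5 = 29 degrees of freedom. Let rho be the baseline/week-4 correlation, which the documents do not give. Assume equal variance at both visits and no effect of sex or age. The sizing text allows two readings of 2.5 s:

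- SD of change: residual SD = 2.5 × √((1 + rho)/2).
- SD of week-4 values: residual SD = 2.5 × √(1 − rho²), and the SD of change is 2.5 × √(2(1 − rho)).

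| rho | ANCOVA, 2.5 s = SD of change | t-test on change | ANCOVA, 2.5 s = SD of week-4 values | t-test on change |
|---|---|---|---|---|
| 0.3 | 0.94 | 0.81 | 0.84 | 0.67 |
| 0.5 | 0.90 | 0.81 | 0.90 | 0.81 |
| 0.7 | 0.86 | 0.81 | 0.98 | 0.95 |

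**5. ANCOVA for the bounded 0–24 score.** Integer scores were simulated with baseline at least 8, the plan's allocation, mean 10–18, SD 4–5 and correlation 0.3–0.7 (all but the first two assumed). ANCOVA type I error was 0.046–0.060.

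**The case against.** The best defence is that the plan settles more than the methods section shows. The hypotheses fix change from baseline to week 4 as the quantity for both endpoints, and the sizing names a t-test on FTBUT change, so that test could be taken as implicitly primary. The first half stands. A reader might infer that the plan leaves open whether change or the raw week-4 value is analysed; it does not, and a two-arm ANOVA of change is the same test as the t-test. The second half does not stand. The t-test is named only for sizing and only for FTBUT, and item 18 prescribes a different between-arm test.

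The defence is also right that the quantified harm is modest: roughly 9–12% disagreement and a type I error of 0.06–0.07, both dependent on assumed strata.

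Four other stronger readings are not supported:

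- That the sample size is wrong. It reproduces exactly.
- That stratifying must lose power. Prognostic strata can offset the loss, so its sign is unknown.
- That leaving sex and age out of the tests is an error. The plan's reason for matching on them is that "these parameters affect dry eye parameters such as marginal changes and meibomian gland secretion", which concerns levels. If they shift both visits equally, an unadjusted test on change loses nothing; if they affect the change itself, it is conservative.
- That the reference to pairs of groups contradicts the two-arm design. Two arms form one pair; the wording is merely loose.

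**Conclusion.** The concern holds on two facts in the text: the strata of the between-arm CMH test are undefined, and neither primary endpoint has a designated primary test. The power of 0.807 therefore belongs to a test that the analysis section does not list. These defects stand whatever the simulations show, and they should be corrected before unmasking. The size figures illustrate the consequence under normal data and two or three non-prognostic strata, none of which the documents specify. The conclusion is limited to the text available for review, in which the methods items run on directly into Confidentiality.

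**What to change.** **Minimum.** Delete the undefined strata and the within-strata tests for the two primary endpoints, and prespecify one primary test for each.

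**Recommended.** For each endpoint, use an ANCOVA of the week-4 value on treatment, baseline value, sex and age group. With baseline in the model, the treatment estimate is the same as for change, so the stated hypothesis is kept. Place age exactly 50 in one group, since the two age levels leave it out. Add a rank-based covariate-adjusted or stratified sensitivity analysis for the 0–24 secretion score.

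**Acceptable fallback.** Name the two-sample t-test on change as primary. For FTBUT this matches the sizing and the 0.807.

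**Cost.** Wording only; baseline, week-4, sex and age data are already collected. The ANCOVA uses three more degrees of freedom (32 to 29), and its gain depends on correlations that the documents do not give. Sample size estimation would also need a sentence saying that the t-test calculation is not that of the primary ANCOVA. The fallback avoids these costs but forgoes the gain.

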Appendix I: see separate word document titled

Appendix II: Symptom Questionnaires

Demographic Data					
Subject Name	Sex: 🗆 Male 🗆 Female 🛛 Today's Date:				
Subject's Date of Birth: / / / mm dd yy	Visit # Time: Age Subject #				
Race □ White □ Black □ Asi	an 🗆 Hispanic 🗆 Other (specify)				
Symptomatology Questionnaires					
I. Schein Questionnaire, modified by SCCO* DURING THE PAST WEEK:					
1. Do your eyes ever feel dry? □ Never □ Rarely □ Sometimes 	Often All of the time				
 Do you ever feel a gritty or sandy sensation in your eye? Never Rarely Sometimes Often All of the time 					
 3. Do your eyes ever have a burning sensation? Never Rarely Sometimes Often All of the time 					
4. Are your eyes ever red?					

- □ Never □ Rarely □ Sometimes □ Often □ All of the time
- 5. Do you notice much crusting on your lashes?

 Never
 Rarely
 Sometimes
 Often
 All of the time
- 6. Do your eyes ever get stuck shut in the morning?

□ Never □ Rarely □ Sometimes □ Often □ All of the time

Total: _____ (score of greater than 5 indicates dry eye)

* a new category of "never" added for Grade 0, and 0-4 scoring added (4 = all the time) from the questions used by Schein OD, Tielsh JM, Munoz MS, Bandeen-Roche K, West S. Relation between the signs and symptoms of dry eye in the elderly. *Ophthalmol*. 1997; 104: 1395-1401.

II. Symptomatology: Ocular Surface Disease Index (from Allergan)

DURING THE PAST WEEK: Have you ever experienced any of the following?

1. Eyes that are sensitive to light?

 \Box All of the time \Box Most of the time \Box Half of the time \Box Some of the time \Box

None of the time

2. Eyes that feel gritty?

□ All of the time □ Most of the time □ Half of the time □ Some of the time □

None of the time

3. Painful or sore eyes?

 \Box All of the time \Box Most of the time \Box Half of the time \Box Some of the time \Box

None of the time

4. Blurred vision?

 \Box All of the time \Box Most of the time \Box Half of the time \Box Some of the time \Box None of the time

5. Poor vision?

 $\hfill \mbox{ All of the time }\hfill \mbox{ Most of the time }\hfill \mbox{ Half of the time }\hfill \mbox{ Some of the time }\hfill \mbox{ None of the time }\hfill \mbox{ Half of the tim$

Have you had problems with your eyes that limited you in performing any of the

following during the last week?

6. **Reading?**

 \Box All of the time \Box Most of the time \Box Half of the time \Box Some of the time \Box None of the time \Box N/A

7. Driving at night?

 $\hfill \mbox{ All of the time }\hfill \mbox{ Most of the time }\hfill \mbox{ Half of the time }\hfill \mbox{ Some of the time }\hfill \mbox{ None of the time }\hfill \mbox{ N/A}$

8. Working with a computer or bank machine (ATM)?

 $\hfill \mbox{ All of the time }\hfill \mbox{ Most of the time }\hfill \mbox{ Half of the time }\hfill \mbox{ Some of the time }\hfill \mbox{ None of the time }\hfill \mbox{ N/A}$

9. Watching TV?

 $\hfill \mbox{ All of the time }\hfill \mbox{ Most of the time }\hfill \mbox{ Half of the time }\hfill \mbox{ Some of the time }\hfill \mbox{ None of the time }\hfill \mbox{ N/A}$

Have your eyes felt uncomfortable in any of the following situations during the last week?

10. Windy conditions?

 \Box All of the time \Box Most of the time \Box Half of the time \Box Some of the time \Box None of the time \Box N/A

11. Places or areas with low humidity (very dry)?

 \Box All of the time \Box Most of the time \Box Half of the time \Box Some of the time \Box None of the time \Box N/A

12. Areas that are air conditioned?

 $\hfill \mbox{ All of the time }\hfill \mbox{ Most of the time }\hfill \mbox{ Half of the time }\hfill \mbox{ Some of the time }\hfill \mbox{ None of the time }\hfill \mbox{ N/A}$

Total: ______ Analysis of Score: _____

*0-4 scoring (0 = none of the time; 1 = some of the time; 2 = half of the time; 3 = most of the time; 4 = all of the time)

(Sum of Scores for All Questions Answered x 100) \div (total # of Qs answered X 4.)

Note: any "N/A" questions are not counted in the total # of questions answered

Appendix III: Case report form

I. Demographic Data

Patient Name / /				Sex: Male Female	Today's Date:
Patient's Date of Birt	h:	_ /	/	Age Time:	
	mm	dd	уу		

Race
□ White
□ Black
□ Asian.....□ Hispanic.....□ Other (specify) _____

II. Medical, Eye and Contact Lens History, and Medications

Pertinent Ocular History	Current Ophthalmic Medications (please list medications and reason for use, including artificial tears)

Contact Lens History	Ever Worn Lenses? Yes No			
If lens wear, how long since	(for protocol, must have been 12			
stopped wearing?	months of total lens deprivation)			
	Daily Wear? Yes No	How Long (years)		
If Soft (SiHy or Hydrogel)	Overnight Wear? Ves No	How Long (years)		
	Daily Wear? 🗆 Yes 🗆 No	How Long (years)		
If Rigid or Gas permeable	Overnight Wear? Ves No	How Long (years)		

Pertinent Medical History	

Benign Prostatic Hyperplasia (BPH)?	Prostate Cancer Diagnosis? exclusion criteria
🗆 Yes 🗆 No	Yes 🗆 No
Breast Cancer Diagnosis? Yes No	Allergies? Yes No List:
History or Symptoms of Venous	History or Symptoms of
Thromboembolism? Yes 🗆 No	Polycythemia/erythrocytosis: Yes No
e.g., deep vein thrombosis : pain, edema, redness in lower extremity	e.g., erythrocytosis: HA, dizziness, shortness of breath, nosebleeds
e.g., pulmonary embolism: shortness of	e.g., polycythemia: fatigue, itching, HA, sweating
breath	
Hepatic Changes? (mainly jaundice):	Edema: 🗆 Yes 🗆 No
🗆 Yes 🗆 No	
Seborrheic dermatitis? 🗆 Yes 🗆 No	Acne Rosacea? 🗆 Yes 🗆 No
Blood thinners? e.g., wayfarin?	Recent MI or stroke: exclusion criteria
🗆 Yes 🗆 No	□ Yes □ No
Current Systemic Medications	
(please list medications and reason for	
use)	

[figure not shown]
III. Visual Acuity Snellen / LogMAR (spectacles / unaided; circle one)

O.D. 20 / O.S. 20 /

IV. Tear Osmolarity: Measured with TearLab; take greater of R, L value as osmolarity

0.D. _____ 0.S. _____ Visit Osmolarity: _____ (msOms/L)

Interferometry/Blink Analysis (Lipiview, lights dim, warn of flashing lights) V.

VIII. Non-Invasive and Fluorescein Breakup Time

[figure not shown]
Notes:

- alternate eyes, 30 seconds rest between measurements to restore tear homeostatic tear stability; ask patient to blink three *natural* blinks then hold open, use stopwatch
- 2. if fluorescein, use Tiffen Yellow 12 filter, wide beam, minimal beam movement

[figure not shown]
O.D. _____, ____, ____ Average _____ (secs)

O.S. _____, ____, ____ Average _____ (secs)

IX. Ocular Surface Staining, NEI (0 – 3 for each of 5 zones for cornea, 0 -3 for six zones (each eye) for conjunctiva, refer to NEI scale) Integer Grading Only

Use lissamine green for conjunctiva (strip; wet with one drop, shake excess)

Total NEI Staining: cornea and conjunctiva: 0 – 33:

O.D. _____ O.S. ____

XI. Ocular Surface Staining: sketch the stained areas

Efron: overall stain for cornea, conjunctiva, 0 - 4 scale with 0.5-unit increments **Oxford Scheme:** (0 – 5 for each of 3 zones for cornea, nasal, temporal conjunctiva (each eye); refer to separate grading scheme Integer Grading Only

[figure not shown]
Corneal Staining: Fluorescein; 0 - 5 O.D.		O.S
Conjunctival Staining: Lissamine green; 0 O.D.	9 - 10	O.S
Total Staining: Efron, 0 – 4 X 3 = 0 – 12; 0 O.D	cford, 0 – 5 X 3 = 0 - 15	0.S
X. Meibomian Gland Expression, Lower	Eyelid: Q-tip (gentle p	pressure) or MGE
OD	OS	
Expression, Overall Grade: Bron et al., 1991 particles; 3 = inspissated, like toothpaste	scale: 0 = normal, clear; 1	= cloudy; 2 = cloudy with
XI. Meibography Number of images take OD UL	en: OS	UL
LL		LL
XII. Meiboscopy, clinical transilluminator eyelid):	(~8 glands assumed i	in each sector of
Dropout Grade: nasal lower lid	0.D.	O.S.
Dropout Grade: central lower lid		
Dropout Grade: temporal lower lid		
Total Eyelid Dropout Score:		

Dropout: 0 = No Dropout; $1 \le 25\%$; $2 \le 50\%$; $3 \le 75\%$; $4 \le 100\%$; **0.2 grade increments per 5% change**

 XV. Schirmer I without anesthetic (amount of wetting in 5 minutes; < 5 mm = ATD)	O.D. _____ (mm)
 O.S. _____ (mm)

